12.3.2 Immunogenicity or Efficacy Review

An immunogenicity review will be completed by the DSMB to determine the most immunogenic (and safe) MTBVAC dose for dose selection for the Phase III study. This analysis is planned to take place once the last Study Day 182 visit of Cohort 3 has been completed and all available immunology samples across Cohort 1, 2, and 3 at Study D28, D56 and D182 visits have been processed. No unblinding of the clinical and immunology team to the

immunogenicity data analysis is expected for this review. An independent, unblinded biostatistician will complete the analysis on the raw immunogenicity data which will be provided by the immunology team. The independent, unblinded biostatistician will analyse MTBVAC dose selection based on magnitude of MTBVAC-specific CD4 T cell response; Comparison of CD4 T cells responses across increasing doses of MTBVAC and BCG; as well as evaluation of selected MTBVAC dose superiority over BCG vaccination. The results of the analysed immunogenicity data will be provided by the independent, unblinded biostatistician directly to the DSMB in a blinded manner along with the vaccine recipient listing. Sponsor will be provided with the same blinded data for review, excluding the vaccine recipient listing to DSMB meeting will take place to assess the maintain blinding of Cohort 3. The immunogenicity results, as described above, for all cohorts (Cohort 1, 2 and 3) up to Study D182 visit per cohort to determine the most relevant dose for the Phase III study. Unblinding of the clinical team will take place post Study Day 365 visit for all cohorts. In order to maintain data integrity and avoid compromising immunology analysis of samples collected at the last visit (Study Day 365 visit), the immunology team will remain blinded until immunology database lock.

Efficacy is not being assessed in this trial.

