Reflecting the clinical strategy to move straight from the Phase IIa to Phase III study with a single selected dose, the design of the proposed Phase III incorporates three case-driven assessments for futility and efficacy. Such a pathway for the MTBVAC clinical development would allow for the neonatal vaccine to be made available sooner (estimated 5 years) with the potential to offer a greater magnitude of protection compared to current BCG vaccine. Such a saving in time would have a major public health benefit when considering that the BCG vaccine has been reported to have variable protective effect depending on the form of TB and the geographical location. The impact of TB in children is significant: in 2019, over one million (1 190 000) children globally became ill with TB and 230 000 died from the illness and therefore it is prudent to develop a more effective vaccine as soon as possible, within safety and regulatory requirements.

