6.3 Treatment Assignment Procedures

6.3.1 Randomization Procedures

Participants will be randomized using a pre-prepared block randomization schedule, linked to study enrolment number.

Ninety-nine (99) infant participants will be recruited, randomized and allocated into 3 groups: BCG (single dose level 2.5 x 10^5 CFU/0.05 mL, n=24); or MTBVAC at three different dose levels as a single intradermal dose of 2.5 x 10^4 CFU (Cohort 1, n=25), 2.5 x 10^5 CFU (Cohort 2, n=25), and either 2.5 x 10^6 CFU (n=25) or 2.5 x 10^5 CFU (n=13) plus 2.5 x 10^4 CFU (n=12) (Cohort 3) (24 BCG; 75 MTBVAC).

Vaccination of newborns will be staggered to allow gradual evaluation of safety and reactogenicity at each escalation of MTBVAC dose. Progression from the 2.5×10^5 to the 2.5×10^6 CFU dose level, for which safety has not yet been demonstrated, will require that all of the following criteria have been met: (1) no pre-defined pausing rules have been observed at lower MTBVAC dose levels in this trial; (2) favourable review of day 28 safety data of all lower MTBVAC dose groups by the Data Safety Monitoring Board (DSMB); (3) favourable review of safety data from the current pilot Phase 1b infant trial by the DSMB; and (4) favourable review of day 28 safety data for the 2.5×10^6 CFU dose level in QFT negative adults in the parallel adult trial by the DSMB. In the event that any one of these safety criteria are not met, Cohorts 1 and 2 will be expanded so that 33 additional neonates will randomly allocated to receive the 2.5×10^4 CFU dose (n=12), the 2.5×10^5 CFU dose (n=13) or BCG (n=8) by default. If there is a delay in adult data, dose escalation in infants will either be delayed, or Cohorts 1 and 2 be expanded as mentioned above.

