12 STATISTICAL CONSIDERATIONS

12.1 Study Hypotheses

No formal hypothesis testing will be performed, since the trial is not powered to do any formal testing (see sample size section below).

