12.2 Sample Size Considerations

The sample size for this study was selected as being adequate for a preliminary assessment of the safety profile of MTBVAC in neonates, rather than for statistical reasons. The sample sizes of Phase 1 and 2a clinical trials are conventionally not powered to detect rare or infrequent events, but rather common safety events, major safety signals, or important trends. The sample size of 99 infants was selected as adequate for such initial evaluation of the safety profile of MTBVAC, rather than for statistical reasons (17-25).

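### Section 12.3.2 picks a dose on CD4 response and then judges that dose's superiority over BCG in the same infants, which biases the comparison upward by up to about 0.17 SD.

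*Combined protocol and SAP*

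**What the plan says.** Section 12.3.2 (Immunogenicity or Efficacy Review) plans a DSMB review "to determine the most immunogenic (and safe) MTBVAC dose for dose selection for the Phase III study". It takes place after the last Cohort 3 D182 visit, once "all available immunology samples across Cohort 1, 2, and 3 at Study D28, D56 and D182 visits have been processed". The independent, unblinded biostatistician has three tasks on those data:

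- "MTBVAC dose selection based on magnitude of MTBVAC-specific CD4 T cell response";
- a comparison of CD4 responses across the MTBVAC doses and BCG;
- "evaluation of selected MTBVAC dose superiority over BCG vaccination".

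The section gives no time point, summary measure, test, error rate, margin or estimator for the third task, and no allowance for the dose having been chosen on the same data.

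Section 12.1 says: "No formal hypothesis testing will be performed, since the trial is not powered to do any formal testing". Section 12.2 adds: "The sample size of 99 infants was selected as adequate for such initial evaluation of the safety profile of MTBVAC, rather than for statistical reasons". Section 12.4.3 describes the between-group comparisons of the final analysis as informal. Section 12.4 promises a detailed SAP, finalised before database lock. Section 3.2 gives the use of the result: the strategy is to "move straight from the Phase IIa to Phase III study with a single selected dose".

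**The concern.** When the dose with the largest observed mean is chosen, that mean is on average above the dose's true mean, because chance helps decide which dose comes first. Comparing the chosen dose with BCG in the same infants carries that excess into the difference. The ordinary interval around the difference then sits too high.

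Picking the largest response is a legitimate way to choose a dose. The difficulty is reading the same estimate as evidence that the dose beats BCG. The word superiority invites that reading, at the point where a single dose is chosen for Phase III. An overstated advantage could affect how the DSMB and the sponsor see the vaccine against BCG, and any later planning that borrows the estimate.

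The open time point adds to the problem. The detailed SAP need only precede database lock, while this review falls before the Cohort 3 D365 visits, so nothing in the text requires the choice to be made before the data are seen.

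**Working it through.** **Check of the plan's own figure.** Three cohorts of 25 + 8 give 3 × 33 = 99, which agrees with "24 BCG; 75 MTBVAC" (Section 6.3.1). There is no statistical derivation to reproduce, since Section 12.2 says the size was not chosen on statistical grounds.

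**Inputs from the protocol.** Three MTBVAC doses with 25 infants each and 24 BCG infants. Under the default for Cohort 3 there are two doses, with 25 + 12 = 37 and 25 + 13 = 38 infants, and 24 BCG (Section 6.3.1).

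**Assumptions, not in the documents.** Normal response on the analysis scale with SD 1 in every arm; one response variable at one time point; full arms; BCG pooled over cohorts; selection on the largest observed mean alone; no selection adjustment.

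**Standard error of one dose-minus-BCG difference.** √(1/25 + 1/24) = √0.08167 = 0.286 SD.

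**Bias when the three doses are equal.** The expected maximum of three independent standard normals is 3/(2√π) = 0.846. Each dose mean has standard error 1/√25 = 0.2 SD. Bias = 0.846 × 0.2 = 0.169 SD, and 0.169/0.286 = 0.59 of the standard error.

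**Bias under the two-dose default, doses equal.** The expected maximum of two is 1/√π = 0.564. With about 37.5 infants per dose, bias = 0.564/√37.5 = 0.092 SD.

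**Dependence on dose separation.** Simulation, 1,000,000 runs per row. The last column is how often the true difference lies below the unadjusted 95% interval (2.5% if the interval were honest).

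| True dose pattern | Bias (SD) | Truth below interval |
|---|---|---|
| Equal doses | 0.169 | 6.3% |
| 0.1 SD per step | 0.150 | 5.8% |
| 0.2 SD per step | 0.109 | 5.0% |
| 0.3 SD per step | 0.070 | 4.1% |
| 0.5 SD per step | 0.024 | 3.1% |
| 1.0 SD per step | under 0.001 | 2.5% |
| Lowest dose 0.5 SD below two equal doses | 0.118 | 4.8% |
| Two-dose default, equal | 0.092 | 4.4% |

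**If superiority were judged at one-sided 2.5%.** The plan states no such rule. With no dose different from BCG, the selected dose would pass z > 1.96 in about 6% of trials with three doses (0.0626 in the simulation) and 4.4% with two. If each dose were compared only with the 8 BCG infants of its own cohort, the three-dose figure would be 5.2%, with the same 0.169 SD bias.

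**Simultaneous intervals.** For three doses against a shared BCG arm the large-sample Dunnett critical value is about 2.35, and slightly higher with t-based intervals. 2.35/1.96 = 1.20, so intervals are about 20% wider. They remain centred on the same estimates, so the bias in the point estimate is untouched.

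**The case against.** Much of the case on the other side stands.

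- **Contradiction with Section 12.1.** A reader might infer that 12.3.2 flatly breaks the statement that nothing is formally tested. The documents do not support that. Section 12.3.2 names no test, error rate or margin, so its evaluation can be read as descriptive. The wording is ambiguous, and no stated error rate is breached.
- **Best dose and best time point.** A reader might infer that the winner could be picked over three doses and three visits. That would raise the false-positive rate to 12% to 16% and the bias to 0.27 to 0.35 SD, for assumed between-visit correlations of 0.8 to 0.3. No section describes such a rule. The time point is open, which is a reason to fix it, but these figures do not describe the plan.
- **A gate to Phase III.** No section makes superiority over BCG a condition for Phase III. Section 3.2 goes on to say that the proposed Phase III has its own case-driven assessments of futility and efficacy.
- **Selection is not on response alone.** Sections 10.7, 12.3.1 and 12.3.2 bring in safety, and the determination is made by the DSMB. Both may reduce the bias.
- **Dose separation.** The doses are ten-fold apart, and Section 3.2 reports a larger Phase 1b response at a higher dose. The bias may be small, but without an effect size or SD the plan cannot show that it is.
- **Other safeguards.** Section 12.3.2 already plans a comparison across all doses and BCG, so the DSMB does not see only the winner. The detailed SAP is not among the documents and may deal with selection, although nothing requires it to exist before the review.

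None of this removes the winner-only superiority evaluation on the selection data.

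**Conclusion.** The point holds as a bias of limited and uncertain size. Followed as written and without adjustment, Section 12.3.2 yields a selected-dose-minus-BCG difference that is too large on average. The excess is at most about 0.17 SD with three doses and 0.09 SD with two, and close to zero if the doses are well separated.

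These bounds assume one fixed response variable, equal SDs, full arms and selection on the observed mean. The false-positive rates of about 6% and 4.4% also rest on an assumed one-sided 2.5% rule and on no dose differing from BCG, so they illustrate the effect and do not show that a stated level is missed. The relation to Section 12.1 is an inconsistency of wording to be cleared up. The choice of dose itself is not called into question.

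**What to change.** Before the D182 interim, amend Section 12.3.2, or set out the following in a document finalised before that review:

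1. Replace the superiority evaluation of the selected dose with differences and intervals for every MTBVAC dose against BCG.
2. Name one variable and time point in advance. An example is the total-cytokine MTBVAC-specific CD4 response at D182, which the amendment rationale in Section 18.1 relies on. Specify the scale, and show D28 and D56 as supportive.
3. State that the comparison is descriptive, in line with Section 12.1, that the selected dose's estimate is subject to selection bias, and that it supports no superiority claim.
4. If the word superiority is kept, use simultaneous Dunnett-type intervals (critical value about 2.35, slightly higher with t-based intervals, for three doses; recompute for the two-dose default) together with a selection-adjusted estimate. The intervals alone do not remove the bias.

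The cost is wording in the plan and in the interim outputs, and a weaker statement against BCG. Intervals become about 20% wider only if they are made simultaneous. No extra infants, samples or visits are needed, and the ranking of doses by response is unaffected.

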12.4 Final Analysis Plan

The planned statistical analyses for this study are outlined below. A detailed statistical analysis plan will be created and finalized prior to database lock. Any deviations from the planned analyses will be described in the final study report.

12.4.1 Participant Analysis Sets

The full analysis set will include all screened participants. The safety analysis set will include all participants who received investigational product. The immunogenicity analysis set will include all participants who received a complete study vaccination and has at least one evaluable immunogenicity result. Listings of participants who did not complete all trial procedures, such as missed visits or other protocol deviations that may affect the analyses, will be provided for the overall sample and by study arm. No imputation for missing data will be performed. Data will be transformed as appropriate prior to analysis, but results calculated from transformed values will be reported in original units for clarity. This trial is not designed for treatment efficacy analysis, but immunogenicity analyses and analysis of clinical reactogenicity will be reported.

12.4.2 Demographics and Protocol Compliance

Baseline demographic (age, sex, and race) and other baseline characteristics will be summarized using descriptive statistics (at a minimum the following will be reported: means, medians, standard deviations, frequencies and proportions, as appropriate), for the overall sample (Safety Analysis Set) and by study group.

As participant enrollment to each cohort will be conducted based on timing of completion of study eligibility requirements, any imbalance in baseline characteristics between cohorts will also be examined.

Listings of randomized participants with protocol deviations will be provided.

12.4.3 Immunogenicity and Other Immunology Analyses

Immunogenicity will be summarized for all time points as collected and as available. No imputation for missing data will be performed. Data will be transformed as appropriate prior to analysis.

For each of the outputs from the relevant immunology parameters, descriptive statistics including means, standard deviations, medians, and interquartile range, will be determined. Between-group comparisons of means or medians at each time point, as well as changes between time points post revaccination, will be performed (informally) as outlined in the Statistical Analysis Plan.

12.4.3.1 Whole Blood ICS

The primary variables of interest for the assessment of the immune response to the study vaccine will be the frequencies of MTBVAC-specific CD4+ and CD8+ T cells that produce any or a combination of relevant cytokines. Response will be measured by flow cytometry using a qualified whole blood intracellular cytokine staining (ICS) assay (24).

T cell responses will be summarized by treatment group and time point. The difference in T cell response between treatment regimens across all post-immunization time points as measured by percentage CD4 and CD8 responses will also be modeled using linear mixed effects models or other regression models, as appropriate.

12.4.3.2 QFT Gold Plus

Qualitative and quantitative results for the QFT Gold Plus test at each available time point will be summarized using participant count (percentage) summaries and descriptive statistics. The proportions of QFT positive participants at various time points may also be compared using chi-square tests or Fisher's exact tests. Appropriate figures will be used to illustrate the observed responses over time.

12.4.4 Safety Analyses

12.4.4.1 Adverse Events

The primary endpoint is the frequency of adverse events (AEs) by MTBVAC dose compared to BCG. In order to assess the primary endpoint, analysis of the data will be preceded by a

blinded data review meeting in order to address population determination and miscellaneous data queries pertinent to analysis of the primary endpoint.

Safety and reactogenicity data will be evaluated by study arm and cohort in all participants in the safety analysis set. The primary variable for evaluation of safety will be the frequency of unsolicited, solicited adverse events and injection site reactions at all available post-vaccination time points. The number and percentage of participants with adverse events will be summarized by MedDRA system organ class (SOC) and preferred term (PT), as well as by severity and relationship to study vaccine. Informal between-group comparisons will be performed using the Chi-square or Fisher Exact test. The Cochran-Mantel-Haenzel test will be used to compare the effect of dose on reactogenicity (injection site adverse events).

Separate listings will be provided for participants with serious adverse events. SAEs may also be summarized by MedDRA system organ class and preferred term.

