8.4 Final Study Visit

Study Day 365

Allowable window for clinic visit is 365 ±14 days from Study Day 0 visit date.

- 1. Verbally reconfirm consent.
- 2. Update medical history including use of medications.
- 3. Screening for potential new TB exposure and TB symptoms.
- 4. Record feeding practice.
- 5. Vital signs (heart rate, respiratory rate, axillary temperature, weight and recumbent length).
- 6. Focused physical examination.
- 7. Record any serious adverse events (including concomitant medications) and unsolicited adverse events.
- 8. Examine site of injection (includes measurement of redness, swelling, and ulceration) and take a pus swab if discharge present.
- 9. Blood collection for:
 - Immunogenicity WB-ICS
 - QuantiFERON®-TB Gold Plus

Post Cohort Unblinding of Participants Post Study Day 365

Participant, and subsequent clinical team unblinding will occur when all infants in a given cohort have attained their Study Day 365 visit.

- MTBVAC recipients who have tested QFT positive will be given a card stating that they
 have received an investigational vaccine that may interfere with interpretation of future
 IGRA and TST tests.
- BCG rescue dose will be offered to all MTBVAC recipients in this cohort, given that the
 individual recipients have a negative screen for active TB disease and new household
 contacts, and do not have a new positive QFT result at D365. Any MTBVAC recipient
 receiving IPT will be offered the BCG rescue dose after completion of IPT.
- 3. The site will contact the participant's caregiver telephonically (or perform a home visit if no telephone available) 14 days post vaccination with the BCG rescue dose to enquire about the infant's wellbeing and BCG injection site reaction, and respond appropriately to any adverse reaction.

Note: The immunology team will remain blinded until immunology database lock.

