10.1 Specification of Safety Parameters

Safety parameters that constitute the primary outcome measures of the study are described in Section 4.2.1. The time periods for collection of adverse events are as follows.

Unsolicited Adverse Events

Unsolicited adverse events will be collected from informed consent until trial completion.

Solicited Adverse Events

Solicited systemic adverse events will be collected post-vaccination through the Study Day 28 visit (with diary cards to be used for 7 days after vaccination).

Solicited injection site reactions will be collected post-vaccination through the Study Day 56 visit (with diary cards to be used for 28 days after vaccination).

Solicited adverse events are events the participant is specifically asked about. These adverse events are commonly observed soon after receipt of vaccines. For this study, solicited adverse events to be collected include:

- Solicited systemic adverse events:
 - fever, irritability, vomiting, diarrhea, drowsiness, poor feeding, skin rash.
- Solicited injection site reaction adverse events:
 - pain, redness, swelling, ulceration, drainage, and regional lymphadenopathy.

Solicited adverse events of injection site reactions will be considered causally related to investigational product.

All participants' caregivers will be provided a diary card to record axillary temperature and information regarding occurrences of these specific events for the first 7 days (for systemic adverse events) or 28 days (for injection site reaction adverse events) of the solicited adverse event reporting period.

Serious Adverse Events

Serious adverse events will be collected throughout the entire study period (i.e., 365 days post-vaccination).

Site of Injection Examination

Site of injection examinations will be performed at the visits noted in the schedule of events in Appendix A. The following will be assessed at each examination:

• Tenderness/pain, redness, swelling, warmth, ulceration, presence of infection/abscess, crusting, drainage, scarring, and regional lymphadenopathy.

Any of the above-mentioned injection site reactions that meet adverse event criteria according to the Toxicity Table in Appendix C will be recorded as adverse events.

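### Unsolicited AEs are summarised as infants with any event over up to a year with no onset interval, which dilutes an early excess in common events and mixes unequal follow-up at the D182 dose-selection review

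*Combined protocol and SAP*

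**What the plan says.** Section 10.1 closes the solicited events. For systemic events: "Solicited systemic adverse events will be collected post-vaccination through the Study Day 28 visit". For local events: "Solicited injection site reactions will be collected post-vaccination through the Study Day 56 visit". Unsolicited events have no such limit: "Unsolicited adverse events will be collected from informed consent until trial completion". The last scheduled visit is about a year after vaccination (Section 8.4): "Allowable window for clinic visit is 365 ±14 days from Study Day 0 visit date".

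Section 12.4.4.1 makes AE frequency by MTBVAC dose, compared with BCG, the primary endpoint. It names as the primary safety variable the "frequency of unsolicited, solicited adverse events and injection site reactions at all available post-vaccination time points". The tables follow: "The number and percentage of participants with adverse events will be summarized by MedDRA system organ class (SOC) and preferred term (PT"). The same counts are also to be broken down by grade and by assessed causality. On testing, the section says: "Informal between-group comparisons will be performed using the Chi-square or Fisher Exact test". Results are to be evaluated by study arm and by cohort.

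No onset interval, episode count or rate per infant-time is set for unsolicited events. Section 12.4.4.2 is more specific for laboratory and vital-sign values: infants with Grade 3 or higher values are counted at every post-vaccination time point as well as overall. The AE table carries no such instruction.

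Section 12.3.1 bases Phase III dose selection on all safety data available when Cohort 3 has completed D182. Section 8.3 notes that Cohorts 1 and 2 will by then have completed all their visits.

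**The concern.** The percentage of infants with at least one event can only rise with time and cannot exceed 100%. If ordinary infant illness is common, most infants in every arm will have an event by one year, whatever happened in the first weeks. An excess soon after vaccination then adds few new infants to the count, because most of those affected would have been counted later anyway. At stake is the descriptive contrast with BCG for common unsolicited events, which is part of the primary endpoint.

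The wording about all available time points does not settle the matter. It defines no intervals and does not say that the SOC/PT table is split by them. Read as per visit, the D182 and D365 entries would still cover about four and six months.

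The same feature creates a second problem at the D182 review. A cumulative percentage depends on length of follow-up, and the cohorts, which carry the dose levels, will have been followed for different times.

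**Working it through.** **What can be reproduced.** The plan gives no event rate, effect size, alpha or power for this comparison. The only figure to check is the head count: 3 × 25 + 3 × 8 = 75 + 24 = 99, which agrees with Sections 5 and 6.3.1.

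**Inputs.** From the documents: 25 infants per MTBVAC dose (if the top dose is used in Cohort 3), 24 BCG infants (8 per cohort), and follow-up to day 365. Assumed: a constant background rate r of unsolicited events per infant-year, independent events, and a rate tripled by MTBVAC for the first 28 days.

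**Dilution.** With t in years and 28/365 = 0.0767:

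- BCG: P = 1 − exp(−r·t)
- MTBVAC, D0-28: P = 1 − exp(−3r × 0.0767)
- MTBVAC, year: P = 1 − exp(−r − 2r × 0.0767)

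At r = 2:

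- D0-28: 1 − exp(−0.460) = 37% vs 1 − exp(−0.153) = 14%
- Year: 1 − exp(−2.307) = 90% vs 1 − exp(−2) = 86%

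The last two columns give the exact power of a two-sided 5% Fisher test, 25 vs 24. The 5% level is also an assumption, and power serves only as a yardstick.

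| r per year | D0-28, MTBVAC vs BCG | Year, MTBVAC vs BCG | Power, D0-28 | Power, year |
|---|---|---|---|---|
| 0.1 | 2.3% vs 0.8% | 10.9% vs 9.5% | 0.0% | 1.6% |
| 0.5 | 10.9% vs 3.8% | 43.8% vs 39.3% | 2.5% | 5.0% |
| 1 | 20.6% vs 7.4% | 68.4% vs 63.2% | 16% | 5% |
| 2 | 37% vs 14% | 90% vs 86% | 35% | 4% |
| 6 | 75% vs 37% | 99.9% vs 99.8% | 77% | 0% |

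At r = 2 the difference falls from 22.7 to 3.6 points. At r = 0.1 it is 1.5 points in D0-28 and 1.4 over the year, so almost nothing is lost. If the rate only doubles, D0-28 power is 12% to 35% for r = 2 to 6, against about 3% or less over the year.

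**Second model.** Suppose instead that vaccination causes an early event with probability 0.40, so P(MTBVAC) = 1 − (1 − P(BCG))(1 − 0.40). At r = 2 the proportions are 49% vs 14% at D28 and 92% vs 86% at one year. At r = 0.1 the difference is 40 points at D28 and still 36 at one year. The pattern is the same: strong dilution for common events, little for uncommon ones.

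**Unequal follow-up at the D182 review, with no vaccine effect.** P = 1 − exp(−r × 182/365) for Cohort 3, and 1 − exp(−r) for Cohorts 1 and 2.

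- r = 1: 39% vs 63%. Pooled BCG: (16 × 63.2% + 8 × 39.3%)/24 = 55%.
- r = 2: 63% vs 86%. Pooled BCG: (16 × 86.5% + 8 × 63.1%)/24 = 79%.

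If Cohort 3 carries the highest dose, that dose would show the lowest percentage through shorter follow-up alone. The 182 days is close to the minimum: infants enrolled early in Cohort 3 will have been followed for longer at the cut, so the real gap would be somewhat smaller.

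**The case against.** The strongest counter-argument is that this affects few rows of the table and that early safety is watched elsewhere. Much of it stands.

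- The gain from windows is confined to the any-event row and busy SOCs. At 0.5 events per year or fewer, a D0-28 Fisher test does no better than the full-year one.
- The expected early reactions (fever, irritability, vomiting, diarrhoea, drowsiness, poor feeding, rash, and local reactions including regional lymphadenopathy) are already solicited in closed windows.
- The DSMB reviews safety after the Day 28 visits of Cohorts 2 and 3 and may unblind. The pausing rules in Section 10.5 cover related SAEs, repeated related Grade 3 or higher events, and a worrying AE pattern. Severity and relatedness tables are planned, although relatedness is a blinded judgement.
- Section 12.1 disclaims formal testing, so low power alone is no criticism. The loss shows in the percentages themselves, however, and a reader who runs no test would still see 90% against 86%.
- Section 12.4 defers detail to a statistical analysis plan to be finalised before database lock. That makes the gap easy to close, but does not close it.
- Evaluation by cohort would compare Cohort 3 with BCG infants on the same follow-up schedule. This protects that comparison, but with 8 controls, and does not help comparison across doses or with pooled BCG.

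A reader might infer that the unsolicited-AE comparison is uninformative as a whole, or that nearly every infant will have an event. The documents do not support either reading: they give no event rate, and uncommon terms are barely diluted.

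**Conclusion.** The point holds for common unsolicited events. As written, Section 12.4.4.1 yields a cumulative one-year percentage that can reduce a difference of about 23 points in the first month to about 4 points, under an assumed 2 events per infant-year tripled for 28 days. The size rests entirely on assumed rates and effects: dilution is near total at 6 per year and negligible at 0.1. The other safeguards mean that an early signal need not go unseen, so it would be too strong to say that the plan hides it.

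The follow-up imbalance at the D182 review needs no vaccine effect. It assumes that the review uses the same cumulative summary, since Section 12.3.1 prescribes no format, and that Cohort 3 has about 182 days of data. Under 1 to 2 events per year the artefact is about 23 to 24 points.

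Both are worth correcting because the remedy uses data already collected. Neither shows that any figure stated in the plan is wrong.

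**What to change.** In Section 12.4.4.1, or in the detailed analysis plan:

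- Tabulate unsolicited AEs with onset after vaccination, overall and by SOC, by onset interval aligned to the visits (D0-28, D29-56, D57-182, D183-365) for each dose and BCG. Assign the interval from the recorded onset date, not the visit date.
- Give events per infant-time beside the full-period percentages, so that repeat episodes and differing follow-up are visible.
- At the D182 review, compare groups over the same follow-up, counting events with onset up to D182.

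There is no need to make D0-28 the single main comparison. Section 3.2 reports the greatest T-cell response in Phase 1b infants at day 70, outside that window, and the documents do not single out one risk period. Nor are rate models needed: with 24 or 25 infants per arm they would be unstable for most terms, and the descriptive tables suffice.

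The cost is SAP wording and a few extra tables. Section 10.2.1 already requires onset dates to be documented, so no new data, visits or participants are needed.
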